14.1. DERIVATIONS

For patients randomized to a study drug planned to be administered on a daily basis, duration of exposure to study drug, in days, will be computed as follows:

- Duration of exposure (days) = (Date of last dose of study drug – Date of first dose of study drug) + 1

For all other patients (i.e. randomized to a study drug planned to be administered not on a daily basis), duration of exposure to study drug, in days, will be computed as follows:

- Duration of exposure (days) = {[Earliest date of (end of planned study treatment period, hospital discharge or discontinuation from study drug)] – Date of first dose of study drug} + 1

For patients randomized to sub-protocol COV-01-004 only, the average dose per day will be computed as follows:

- Average dose (mg/day) = Total cumulative dose (mg) / duration of exposure (days)

where the total cumulative dose is the computed total cumulative dose (mg) taken by a patient during the course of the study.

15. COMPLIANCE WITH STUDY DRUG

Compliance with study drug will be summarized by treatment arm (breaking down the placebo plus SoC arm by sub-protocol) based on the safety analysis set. In addition to the descriptive summary, the following compliance categories will be presented:

- < 80%;
- ≥ 80% to < 100%
- 100%;
- > 100%.

Compliance data will also be listed.

15.1. DERIVATIONS

For each patient, the compliance will be computed as follows:

- Compliance (%) = (Actual total number of doses / Expected total number of doses) x 100

where:

- Actual total number of doses is defined as the sum of all doses taken through the course of the study
- Expected total number of doses is defined as the sum of protocol-defined doses to be taken through the course of the study and is computed as follows:
 - For patients randomized to a study drug administered on a daily basis:
 - Expected total number of doses = expected number of doses (injections) per day * expected number of days under treatment, where the expected number of days under treatment is defined as: { [Earliest date of (end of planned study treatment period, hospital discharged or discontinuation

from study drug)] – Date of first dose of study drug} + 1

- For patients randomized to a study drug planned to be administered not on a daily basis:
 - Expected total number of doses = Expected number of doses (injections) per day * number of expected administration days between randomization and the earliest of (end of planned study treatment period, hospital discharged or discontinuation from study drug).

For example, if a study drug is planned to be administered once on Day 1 and once on Day 4, the expected total number of doses is 2; unless patient discontinued from study drug or was discharged from the hospital on or after Day 1 but before Day 4, in which case the expected total number of doses is 1. As another example, if the study drug is planned to be administered twice daily on every other day from Day 1 to Day 14, the expected total number of doses is 14; unless patient discontinued from study drug or was discharged from the hospital let say, on Day 10, in which case the expected total number of doses is 10 (i.e., 2 doses [injection] per days * 5 administration days).

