## 5.4 Dose Modifications and Toxicity Management

The reason for dose change of study treatment is to be recorded on the patient's eCRF.

The dose of apremilast or placebo is to be reduced as follows:

- Study treatment administration should be reduced to QD in patients with creatinine clearance of < 30 mL/min (estimated by the Cockcroft-Gault equation).
- If gastrointestinal adverse events associated with the start of therapy are not mitigated with antiemetics and/or antidiarrheals, study treatment dosing may be reduced to QD for 1 to 3 days. Thereafter, the dose should be increased to 30 mg BID.
- Study treatment is to be withheld if a patient requires renal replacement therapy, such as hemodialysis. Treatment may be resumed the next day if renal replacement therapy is no longer needed, if prior to Day 14. If dosing is resumed, daily dose will be based on the patient's creatinine clearance.

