14. EXPOSURE TO STUDY DRUG

Patients randomized to sub-protocol COV-01-005

Patients randomized to zilucoplan plus standard of care (SoC) and placebo plus SoC treatment arms of COV-01-005 sub-protocol will receive a single daily dose of 32.4 mg of the study drug (prefilled syringes containing 0.81 mL of zilucoplan or placebo, as appropriate) administered by subcutaneous (SC) injection in the abdomen (preferred site), thigh or upper arm.

The daily administration of study treatment will start on Day 1 (baseline) and continue to Day 14 or until hospital discharge, whichever occurs first. If the patient is discharged before 14 days of treatment, zilucoplan or placebo should be stopped at time of discharge or 24 hours before discharge.

Reason for dose modification of study drug (i.e. dose interrupted or drug withdrawal) will be captured in the *Exposure* page of the eCRF.

Patients included in the control arm of COV-01-005 sub-protocol who were randomized to the placebo plus SoC group of a sub-protocol other than COV-01-005

It is to be noted that the planned duration of exposure to a study drug, planned frequency of administration of the study drug, and planned route of administration of the study drug will vary from one sub-protocol to the other, but similar information as for COV-01-005 sub-protocol will be captured on the *Exposure* page of the eCRF of these other sub-protocols.

Exposure to study drug

The exposure to study drug will be summarized by treatment arm (breaking down the placebo plus SoC arm by sub-protocol) based on the safety analysis set as follows:

[figure not shown]
- Duration of exposure:
 - Duration of exposure (days) as a continuous variable;
 - Duration of exposure (days) as a categorical variable: 1 to 3, > 3 to 7, > 7 to 14, and > 14;
 - Total number of doses received as a continuous variable, where the total number of doses received is defined as the total number of doses received by each patient, not the total number of doses received across all patients.

CCI

PPD

Version Number: Amendment 2, v1.0
Version Date: 28-Jul-2021

CCI

- Dose modifications:
 - Number and percentage of patients with at least one interrupted dose;
 - Number and percentage of patients with at least one dose interruption by reason for dose interruptions:
 - Adverse events;
 - Other.
 - Total number of dose interruptions as a continuous variable, where the total number of dose interruptions is defined similarly to the total number of doses received;

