15.1. DERIVATIONS

For each patient, the compliance will be computed as follows:

- Compliance (%) = (Actual total number of doses / Expected total number of doses) x 100

where:

- Actual total number of doses is defined as the total number of doses (injections) taken (received) through the course of the study;
- Expected total number of doses is defined as the total number of protocol-defined doses (injections) to be taken (received) through the course of the study and is computed as follows:
 - For patients randomized to a study drug administered on a daily basis:
 - Expected total number of doses = Expected number of doses (injections) per day * expected number of days under treatment, where the expected number of days under treatment is defined as: {[Earliest date of (end of planned study treatment period, hospital discharged or discontinuation from study drug)] – Date of first dose of study drug} + 1

- For patients randomized to a study drug planned to be administered not on a daily basis:
 - Expected total number of doses = Expected number of doses (injections) per day * expected number of administration days between randomization and the earliest of (end of planned study treatment period, hospital discharged or discontinuation from study drug)
- For example, if a study drug is planned to be administered once on Day 1 and once on Day 4, the expected total number of doses is 2; unless patient discontinued from study drug or was discharged from the hospital on or after Day 1 but before Day 4, in which case the expected total number of doses is 1. As another example, if the study drug is planned to be administered twice daily on every other day from Day 1 to Day 14, the expected total number of doses is 14; unless patient discontinued from study drug or was discharged from the hospital let say, on Day 10, in which case the expected total number of doses is 10 (i.e., 2 doses [injection] per day * 5 administration days).

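### For daily drugs, the COV-01-004 and COV-01-005 compliance formulas count doses that were not due, so fully adherent patients can score below 100%, and below 80% on very short stays

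*SAP*

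**What the plan says.** Both SAPs use "Compliance (%) = (Actual total number of doses / Expected total number of doses) x 100". The denominator is introduced as what the protocol requires; in the COV-01-004 SAP, "Expected total number of doses is defined as the sum of protocol-defined doses to be taken through the course of the study and is computed" by one of two branches.

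- **Daily drugs.** COV-01-004 SAP 15.1 has "Expected total number of doses = expected number of doses (injections) per day * expected number of days under treatment"; COV-01-005 SAP 15.1 has "Expected total number of doses = Expected number of doses (injections) per day * expected number of days under treatment". Days under treatment are a date difference plus one, from first dose to whichever comes first of planned end, discharge or stopping the drug.
- **Drugs not given daily.** Only scheduled administration days before that end point count. A Day 1/Day 4 drug has 2 expected doses, or 1 if the patient leaves before Day 4. For twice-daily dosing on alternate days to Day 14 the answer is 14, or, with discharge on Day 10, "in which case the expected total number of doses is 10 (i.e., 2 doses [injection] per days * 5 administration days".

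The dosing rules that feed the daily branch are these.

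- Apremilast is twice daily, about 12 hours apart, for 14 days or until discharge (COV-01-004 sub-protocol 5.1 and 5.2).
- Section 5.4 of that sub-protocol adds "Study treatment administration should be reduced to QD in patients with creatinine clearance of" less than a stated limit, a short once-daily period for gastrointestinal events, and withholding during renal replacement therapy.
- For zilucoplan patients discharged before 14 days, COV-01-005 SAP Section 14 says "zilucoplan or placebo should be stopped at time of discharge or 24 hours before discharge".

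On reporting, the COV-01-004 SAP states: "Compliance with study drug will be summarized by treatment arm (breaking down the placebo plus SoC arm by sub-protocol". The classes in both SAPs are below 80%, 80% to below 100%, 100%, and above 100%.

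**The concern.** The daily branch does not compute what its lead-in defines. It charges a full day's doses to the first day and to the discharge day, whether or not they fell due. The alternate-day and Day 1/Day 4 examples follow the opposite principle: a dose that has not come due by discharge is not expected. Neither example covers a daily drug or a partial day.

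The two clocks in the same SAPs also differ. For daily drugs, duration of exposure (Section 14.1) ends at the last dose, while expected doses run to discharge. A zilucoplan patient last dosed the day before an L-day stay ends has L − 1 days of exposure and L expected doses.

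At stake is whether the compliance table means what it says. The shortfall is a fixed number of doses over a denominator that grows with stay, so it is largest in short stays. It also differs by regimen: an adherent two-infusion placebo patient scores 100%, while an adherent patient on a daily placebo in the same shared control arm may not.

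**Working it through.** **Reproducing the plan's own examples.** Alternate days from Day 1 to Day 14 are 1, 3, 5, 7, 9, 11, 13: 7 × 2 = 14. To Day 10 they are 1, 3, 5, 7, 9: 5 × 2 = 10. Day 1/Day 4 gives 2, or 1. All agree with the SAP.

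**Daily branch.** Let L be the calendar days from first dose to discharge, inclusive, with discharge before the planned end. Expected doses are 2L for apremilast and L for zilucoplan. If k of these were not due and every due dose was taken, compliance is (2L − k)/2L or (L − k)/L.

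- Apremilast, k = 1: evening start, or discharge before the evening dose.
- Apremilast, k = 2: both.
- Zilucoplan, k = 1: last dose the day before discharge, not recorded as discontinuation.

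| L | Apremilast k = 1 | Apremilast k = 2 | Zilucoplan k = 1 |
|---|---|---|---|
| 2 | 3/4 = 75.0% | 2/4 = 50.0% | 1/2 = 50.0% |
| 3 | 5/6 = 83.3% | 4/6 = 66.7% | 2/3 = 66.7% |
| 4 | 7/8 = 87.5% | 6/8 = 75.0% | 3/4 = 75.0% |
| 5 | 9/10 = 90.0% | 8/10 = 80.0% | 4/5 = 80.0% |
| 8 | 15/16 = 93.8% | 14/16 = 87.5% | 7/8 = 87.5% |

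So scores are below 80% for L up to 2 (k = 1) and up to 4 (k = 2, or zilucoplan). At L = 5 the value is exactly 80.0%, which belongs to the next class up. An evening start with discharge before even the morning dose leaves three not due; (2L − 3)/2L is still below 80% at L = 7 (11/14 = 78.6%).

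**Cases with little or no shortfall.** A morning start with the evening dose taken on the last day gives 100%. For apremilast patients still treated at Day 14, the planned end caps the count and only the first day can be partial: 27/28 = 96.4%.

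**Directed reductions, if expected stays at two per day.** Once daily throughout: L/2L = 50%. Once daily from Day 9 to Day 14: (16 + 6)/28 = 78.6%. Three once-daily days only: 11/14 = 78.6% over 7 days, 25/28 = 89.3% over 14.

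**How many stays are this short.** The documents give no length-of-stay distribution. As an assumption, take the planning medians for recovery (11 days active, 15 placebo; Master SAP 7.1) as a proxy for discharge, with exponential times. By Day 4, 1 − 2^(−4/11) = 22.3% and 1 − 2^(−4/15) = 16.9% have left. For the four-day limit these are ceilings, since only patients with the relevant doses not due are affected.

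**The case against.** The strongest case for leaving the text alone has four parts.

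1. The lead-in speaks of protocol-defined doses. Once daily while a reduction applies is protocol-defined, so the doses-per-day term could be read as 1 for that period. This stands as a possible reading. The SAP does not state it, so the 50% figure is conditional.
2. A zilucoplan stop the day before discharge could be recorded as discontinuation of study drug. That earlier date would then end the count and the patient scores 100%. This also stands, and the SAP does not say which date applies.
3. Directed reductions are not hidden. Section 14 of the COV-01-004 SAP tabulates reductions and interruptions by reason, including low creatinine clearance and renal replacement therapy, and placebo is broken down by sub-protocol.
4. Compliance is only summarised and listed. No analysis set in the Master, COV-01-004 or COV-01-005 SAP uses it, and the COV-01-005 SAP (Section 16) plans no efficacy inference.

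These points limit the size of the problem. They do not answer the partial-day error for apremilast, where the stated arithmetic gives the wrong number whichever of these readings is taken.

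A reader might also infer more than the documents support. It is not true that adherent short-stay patients generally fall below 80%: that needs the specific timings shown above. Nor do the documents show that an agent which shortens stay would look materially less adherent. Under the proxy the arms differ by 22.3 − 16.9 = 5.4 points in stays of up to 4 days, even if every such patient met the worst timing. No analysis in the plan builds on compliance, so a misleading dilution argument is hypothetical.

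**Conclusion.** The point holds in limited form. The daily branch contradicts its own lead-in and the not-yet-due principle of the Day 1/Day 4 example, so a fully adherent patient can be reported below 100%. Classification below 80% is possible for apremilast stays of up to 2 days with one dose not due, or up to 4 days with an evening start and discharge before the evening dose. It is also possible for zilucoplan stays of up to 4 days when the last dose is the day before discharge and is not recorded as discontinuation.

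Separately, the treatment of directed apremilast reductions and withholding is unstated rather than shown to be wrong.

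The conclusion assumes that every due dose was taken and that the formula is programmed as written. The effect is confined to the compliance table and listing, so this is a minor correction. No dosing or stopping rule is questioned.

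**What to change.** In COV-01-004 SAP 15.1 and COV-01-005 SAP 15.1, count only doses due.

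- **First day:** count from the recorded first-dose time, using the roughly 12-hour spacing for twice-daily drugs.
- **Discharge day:** count a dose as expected only if it was given or, if discharge time is available, only if it was due before discharge. Simply never counting the zilucoplan discharge-day dose would not work: a patient who received it, as the sub-protocol permits, would score L/(L − 1), or 4/3 = 133% at L = 4.
- **Directed reduction or withholding:** while one is recorded on the Exposure page, use the frequency then in force.

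Most inputs are already collected. Dose dates and times go into the eCRF (master protocol 6.4; COV-01-004 sub-protocol 5.2), and modification reasons are on the Exposure page (Section 14 of both SAPs). The documents show hospitalization dates but do not confirm a discharge time, which is why the rule for doses given is offered first.

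The cost is a slightly more complex derivation. Under the rule for doses given, a genuinely missed discharge-day dose would no longer count as non-adherence.

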16. EFFICACY ENDPOINTS

[figure not shown]
Efficacy analyses are described in the Master COV-01 SAP.

17. SAFETY ENDPOINTS

17.1. ADVERSE EVENTS

In addition to the safety analyses described in the Master COV-01 SAP, the following analyses will be repeated for the subgroup of patients defined in Section 7.7 based on the safety analysis set:

- Overview of treatment-emergent adverse events (TEAEs);
- TEAEs by maximum Common Terminology Criteria for Adverse Events (CTCAE) grade, System Organ Class and Preferred Term (PT);

- TEAEs with a CTCAE grade ≥ 3 by System Organ Class and PT;
- Fatal TEAEs by System Organ Class and PT;
- Serious TEAEs by System Organ Class and PT;
- Most common serious TEAEs by PT, where a most common is defined as at least 1% in at least one treatment arm;
- TEAEs leading to dose modification by System Organ Class and PT;
- TEAEs leading to discontinuation of study drug by System Organ Class and PT;

Patients excluded from the subgroup defined in Section 7.7 will be flagged in the listings of all fatal AEs, all SAEs, and all AEs leading to permanent discontinuation of study drug.

Refer the Master COV-01 SAP Section 18.1 for additional details about these summaries and listings.

17.2. LABORATORY EVALUATIONS

Analysis of laboratory evaluations is described in the Master COV-01 SAP.

17.3. VITAL SIGNS

Analysis of vital signs is described in the Master COV-01 SAP.

17.4. ECG EVALUATIONS

Analysis of electrocardiogram (ECG) evaluations is described in the Master COV-01 SAP.

17.5. PHYSICAL EXAMINATION

Analysis of physical examination is described in the Master COV-01 SAP.

CCI

[Redacted]

[figure not shown]
PPD

[Redacted]

Version Number: Amendment 1, v1.0
Version Date: 23Apr2021

CCI

[Redacted]

18. PHARMACOKINETICS

PK concentrations of apremilast will be summarized and listed by visit and timepoints based on the PK analysis set. In addition to the descriptive statistics mentioned in Master COV-01 SAP Appendix 2, the coefficient of variation (CV%), geometric mean, geometric standard deviation (SD), and geometric CV% will also be provided for the PK concentrations. Concentrations that are below the limit of quantification (BLQ) will be treated as a numeric value of zero.

PK concentrations of apremilast will be summarized for the following time categories:

- 0 - < 3 hours post morning administration of study drug;
- 3 - <6 hours post morning administration of study drug;
- 6 - < 9 hours post morning administration of study drug;
- 9 - <12 hours post morning administration of study drug
- 0 - < 3 hours post evening administration of study drug;
- 3 - <6 hours post evening administration of study drug;
- 6 - < 9 hours post evening administration of study drug;
- 9 - <12 hours post evening administration of study drug.

Scatter plots of plasma concentrations against the time since last dose, in hours, will be provided for each day and each dose of study drug (i.e., Day 8 post morning administration of study drug, Day 8 post evening administration of study drug, Day 15 post morning administration of study drug, and Day 15 post evening administration of study drug).

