### **4.1 Pharmacokinetic Assessments**

Blood will be collected on Days 8 and 15 for assessment of apremilast concentrations. The date and time of the pharmacokinetic sample collection will be documented on the electronic case report form (eCRF).

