18. PHARMACOKINETICS

[figure not shown]
PK concentrations of Lanadelumab-IV will be summarized by visit and timepoint (refer to Section 3.2) based on the PK analysis set (refer to Section 5.2) overall and broken down further by the ordinal scale for clinical severity score at baseline (2 or 3 to 5). Concentrations that are below the limit of quantification (BLQ) will be treated as a numeric value of zero and will be excluded from the geometric statistics. All PK concentrations will be reported and analyzed with 3 significant figures. For the reporting of descriptive statistics, the mean, standard deviation, standard error (if reported), and confidence interval (if reported) will be presented to one digit more precision than the source

CCI

PPD

Version Number: Amendment 3, v1.0
Version Date: 23-Jul-2021

CCI

data. The minimum, median, and maximum will be presented to the same precision as the source data. Coefficient of variation will always be reported to 2 decimal places.

For Day 1, PK concentrations of Lanadelumab-IV will be summarized for the pre- and post-infusion separately.

Post-dose timepoints will be presented for Days 4, 7, 15, 29, and day of discharge as PK blood samples can be collected at any time during each of these days.

PK concentrations will be listed according to nominal time points scheduled.

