18. PHARMACOKINETIC ASSESSMENTS

Concentrations of zilucoplan will be summarized descriptively at each scheduled assessment based on the PK analysis set (refer to Section 5.1). Geometric mean (geoMean), geometric coefficient of variation (geoCV) and 95% CI for the geoMean will also be presented in the summaries of zilucoplan concentration data. Geometric coefficient of variation will be reported as a percentage to 1 decimal place and the 95% CI for the geoMean will use the same number of decimal places as the geoMean. It will be left blank if the geoCV is 0.

When reporting individual zilucoplan concentration data in listings and presenting summary statistics in tables, the following rules will apply:

CCI		Version Number:	Amendment 2, v1.0
PPD		Version Date:	28-Jul-2021

CCI [Redacted]

- Missing data should be reported as ‘NV’ (no value) in the listings;
- Concentrations below the lower limit of quantification (LLOQ) should be reported as BLQ (below the limit of quantification) in the listings;
- To calculate summary statistics, BLQ values should be set to half the LLOQ value and missing values should be excluded;
- When the total number of BLQ and missing values exceeds one third of the total then only minimum and maximum should be reported for this scheduled assessment. Other summary statistics should be reported as missing (“-“). The minimum should be reported as BLQ;
- When the mean value includes one or more replaced BLQ values then a footnote should be included to say “contains one or more BLQ values replaced by half the LLOQ value”;
- A minimum of 3 values are required to calculate summary statistics. If only 2 values are available, then these should be presented as the minimum and maximum with other summary statistics reported as missing (“- “).

Zilucoplan concentrations will be listed.

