18.1. DERIVATION

The geoCV, in percentage, will be calculated using the following formula where SD is the standard deviation from the log-transformed data:

- $GeoCV (\%) = \sqrt{\exp(SD^2) - 1} \times 100$

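### The apremilast SAP sets BLQ concentrations to zero and asks for geometric statistics without excluding the zeros, so these cannot be computed properly in any cell that contains a BLQ value

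*SAP*

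**What the plan says.** The COV-01-004 SAP, Section 18, adds to the usual descriptive statistics: "the coefficient of variation (CV%), geometric mean, geometric standard deviation (SD), and geometric CV% will also be provided for the PK concentrations". The sentence that follows gives the BLQ rule: "Concentrations that are below the limit of quantification (BLQ) will be treated as a numeric value of zero". Section 18 calls for summaries by visit and timepoint and lists eight time categories, four after the morning dose and four after the evening dose, the last in each set ending before 12 hours. Section 18.1 derives only the time since dose. Neither section says how a zero enters a statistic computed on the log scale.

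The other two sub-protocol SAPs do deal with this:

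- COV-01-001 (lanadelumab), Section 18, uses the same zero rule but completes it. BLQ values "will be treated as a numeric value of zero and will be excluded from the geometric statistics".
- COV-01-005 (zilucoplan), Section 18, uses a different rule: "To calculate summary statistics, BLQ values should be set to half the LLOQ value and missing values should be excluded". It also reports only the minimum and maximum when BLQ and missing values together exceed one third of the total. Section 18.1 of that SAP defines the geometric CV, "where SD is the standard deviation from the log-transformed data".

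The Master SAP, Section 17.2, has a rule for results reported as below a limit, but it is written for quantitative laboratory tests, not PK concentrations.

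**The concern.** A geometric mean is the antilog of a mean of logs, and zero has no logarithm. Two adjacent sentences of Section 18 therefore give instructions that cannot both be carried out in a cell that contains a BLQ value. This is more than a missing detail: a rule is stated, and following it gives a meaningless result.

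The programmer would then have to choose between printing 0, printing missing, dropping the value or substituting something for it, and the SAP supports none of these over the others. The choice would be made after concentrations are available, and as the working shows, the options give very different numbers. At stake is whether the apremilast concentration tables are reproducible and readable. No test, efficacy estimate or interim decision depends on them.

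**Working it through.** **Inputs from the documents**

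- BLQ set to 0, with geometric mean, SD and CV% required: COV-01-004 SAP, Section 18.
- Geometric CV formula, 100 × √(exp(SD²) − 1) with SD on the log scale: COV-01-005 SAP, Section 18.1. The COV-01-004 SAP gives no formula, so I assume the same one.
- Sampling: "Blood will be collected on Days 8 and 15 for assessment of apremilast concentrations" (COV-01-004 sub-protocol, Section 4.1). The Day 15 visit has a window of ±2 days (its Section 1.2).
- Dosing: 14 days at most, and less if the patient is discharged, dies or discontinues (its Section 5.1).
- No LLOQ and no expected BLQ frequency are given. There is no figure of the plan's own to reproduce.

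**General result**

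For n concentrations, GM = (x₁ × … × xₙ)^(1/n) = exp(mean of ln x), and geometric SD = exp(SD of ln x). If one x is 0, the product is 0, so GM = 0 whatever the other values are. Computed through logs, ln 0 is undefined, so the SD of ln x does not exist, and neither do the geometric SD and geometric CV%. The arithmetic CV, 100 × SD / mean, is defined as long as the mean is above zero, so it fails only if every value in the cell is BLQ.

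**Illustration (all concentrations assumed)**

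Take nine quantifiable values in ng/mL: 300, 400, 450, 500, 550, 600, 700, 800 and 900. Their sum is 5,200. The mean of ln x is 6.307, so GM = exp(6.307) ≈ 548.5. The SD of ln x is 0.348, so the geometric SD is exp(0.348) = 1.42 and the geometric CV is 100 × √(exp(0.348²) − 1) = 35.8%. Now add one BLQ sample. The arithmetic mean becomes 5,200 / 10 = 520.0.

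| Handling of the BLQ value | Arithmetic mean | Arithmetic CV% | Geometric mean | Geometric SD | Geometric CV% |
|---|---|---|---|---|---|
| No BLQ sample (n = 9) | 577.8 | 33.5 | 548.5 | 1.42 | 35.8 |
| Zero, as written in COV-01-004 (n = 10) | 520.0 | 49.7 | 0 | undefined | undefined |
| Zero for arithmetic, excluded from geometric (COV-01-001 rule) | 520.0 | 49.7 | 548.5 | 1.42 | 35.8 |
| Half LLOQ (COV-01-005 rule), LLOQ 1 assumed | 520.05 | 49.7 | 272 | 9.4 | 1219 |
| Half LLOQ, LLOQ 2 assumed | 520.1 | 49.6 | 292 | 7.5 | 765 |
| Half LLOQ, LLOQ 10 assumed | 520.5 | 49.4 | 343 | 4.6 | 302 |

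The second row does not depend on the values chosen. The rows below it do.

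**Where a BLQ value could come from**

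- Within a time category, a BLQ value would have to come mainly from a missed, withheld or poorly absorbed dose. Section 5.4 of the sub-protocol provides for treatment being withheld during renal replacement therapy. The PK analysis set (COV-01-004 SAP, Section 5.1) asks only for one measured concentration, so such patients remain in it.
- Dosing ends by Day 14 while the second sample may be drawn as late as Day 17. Most samples taken after the last dose fall outside the eight categories, which stop short of 12 hours. They would enter only a by-visit summary that is not split by time category. The wording of Section 18 leaves open whether one is produced.

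**The case against.** The strongest reply is that the defect may never show. Section 2.2 of the sub-protocol cites exposure of about 550 ng/mL at steady state on the study regimen, so a BLQ result within 12 hours of a dose taken as planned would be unusual. Patients who stop because they go home are then seen by telemedicine and are unlikely to supply a late sample. If the software treats ln 0 as missing throughout, the result is the same as under the COV-01-001 rule. Individual concentrations are also listed and plotted, and Section 8.6 of the Master Protocol says that PK analysis is neither a primary nor a secondary objective.

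Most of this stands, and it limits the size of the point. It does not remove the point: the SAP does not specify that zeros drop out of log-scale statistics, and a table should not depend on what a program happens to do with an undefined value.

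A reader might also infer three stronger things that the documents do not support:

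- That every CV in the table fails. The ordinary CV% named in the same sentence survives a single zero.
- That samples drawn after dosing ends will spoil the time-category summaries. Most of them belong to no category.
- That the two sister rules are equivalent repairs. Half LLOQ would also replace the zero rule for the arithmetic statistics. In the example it gives a geometric mean of 272 to 343 against 548.5. Copying that one line would leave out the COV-01-005 safeguard for cells with many BLQ values.

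**Conclusion.** The rule is wrong as written, and the point is minor. Section 18 gives a geometric mean of 0 (or missing) and an undefined geometric SD and geometric CV% in any cell with at least one BLQ value. That conclusion is purely arithmetical and rests on no assumption about the data. Whether it occurs, and in how many cells, cannot be judged from the documents. The size of the differences between handling rules rests on the assumed concentrations and on assumed LLOQs of 1 to 10 ng/mL.

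The COV-01-001 SAP starts from the same zero rule and adds the exclusion clause, so what is absent here is easy to identify. The consequence is confined to descriptive PK tables. The documents give no support for reading it as a threat to the efficacy or safety conclusions.

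**What to change.** Add one sentence to Section 18 of the COV-01-004 SAP, taken from the COV-01-001 SAP: BLQ values count as zero in the arithmetic statistics and are left out of the geometric mean, geometric SD and geometric CV%. Report the number of BLQ values in each cell, because the arithmetic and geometric statistics will then rest on different numbers of samples and the geometric ones will describe quantifiable concentrations only.

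The cost is one sentence in the SAP and one count per cell in the PK table shell. No data collection, sample size or other analysis changes. The sentence should be in place before the primary analysis, when Section 4 of this SAP schedules these outputs.
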